11.3.1. Patient & Caregiver Assessment Process

11.3.1a. BEFORE BASELINE VISIT:

Site study staff will telephone the participant to:

- Confirm scheduled visit with the oncology physician.
- Confirm that the patient and caregiver completed the screening surveys before the oncology physician visit and remind them to bring the surveys in with them.
 - Schedule the patient to come in to meet with site study staff at least 45 minutes prior to the oncology physician visit in order to complete study procedures. Allow for more time if patient and caregiver communicate(s) that surveys have not been completed. Only patients who complete GA procedures can be registered for the study.

11.3.1b. AT THE BASELINE VISIT:

- If the patient’s screening surveys have not been completed prior to the patient coming in, complete them now.
- If the caregiver’s surveys have not been completed prior to the caregiver coming in, complete them now.
- If not complete staff should administer cognitive, physical performance, and nutrition assessment.
- If not complete, staff should complete CRA study forms.

- If not complete, complete baseline surveys. The baseline surveys do not need to be completed prior to registration, but should be completed on the day of the baseline visit. For example, patients can complete baseline surveys while receiving cancer treatment that same day.
- Score each GA measure as taught in the training procedures. If assistance is needed for scoring, contact the URCC NCORP Research Base.
- Patients who have at least one abnormal GA score other than polypharmacy can move forward with the study.
- After the GA and the above steps are complete, the baseline registration procedures can be completed for the patient and caregiver (refer to section 6, Registration).
 - Registration must occur prior to baseline study visit with the oncology physician.
- Prior to the study visit with the oncology physician, if depression (GDS) or cognition (BOMC) assessments score ≥ 11 , inform patient's oncology physician as follows:
 - Usual Care arm -- inform oncology physician with template as per training.
 - Intervention arm -- information on cognitive impairment or depression is included in summary (see section 11.3, *Intervention Procedures*).

11.3.2. Intervention Procedures (Only for sites randomized to the intervention arm)

11.3.2. a. AT THE BASELINE VISIT:

- After the patients have been registered for the study, enter the GA scores into the mycarg.org website or if no internet is available, contact the URCC NCORP Research Base to assist.
- After entering the GA scores, print the built pdf packet specific to that patient.
- Present GA summary form and recommendation forms to oncology physician to review just prior to baseline patient-oncology physician visit. Study staff can assist the oncology physician in the completion of the forms. Study and clinical staff can assist in implementing GA-driven recommendations after physician approves them.
 - Information on cognitive impairment or depression is included in the summary.
 - The oncology physician MUST review and sign the summary form and recommendations forms.
 - GA recommendations that are planned by the oncology physician for the patient should be check-marked by the end of the visit.
- Three copies of the GA summary and GA recommendations forms should be made: one should be provided to the patient, one should be provided to the caregiver (if requested), and one should be retained in the study chart.
- The original forms should be sent into the URCC Research Base.

11.3.3. Oncology Physician Assessment for Patients: After the audio-recorded baseline visit, oncology physicians will complete a brief survey (on paper) to capture factors that influenced the decision-making process for the patient's plan.

11.3.4. Submitting Materials to the URCC Research Base:

11.3.4a. After the audio-recorded baseline visit, site study staff should ensure the forms below are completed and submit them to the URCC Research Base:

- All oncology physician, patient and caregiver assessments from above
- All CRA Study Forms
- Audio-recordings (submitted and stored as per training) with Audio-recording Data Form
- Intervention summary and recommendation forms (if applicable).

11.3.5. Audio-recordings (for both intervention and usual care)

11.3.5a. The first visit with the oncology physician following the completion of GA measures will be audio-recorded for analysis of content and process of communication.

11.3.5b. Site study staff need to ensure that two audio-recorders are on and working during the visit, but do not need to be present in the room during the visit.

11.3.5c. Site study staff will submit audio-recordings as per training and complete the audio-recording data form.

11.4. Follow-up Visits

11.4.1. Visits will occur 4-6 weeks after the baseline audio-recorded visit, 3 months after the baseline audio-recorded visit (10-14 weeks), and 6 months after the baseline audio-recorded visit (20-24 weeks).

11.4.1a. BEFORE EACH FOLLOW-UP VISIT:

Study staff will telephone the participant to:

- Confirm scheduled visit with the oncology team. The visit does not need to be scheduled with the oncology physician.
- Confirm that the patient and caregiver completed the surveys.
 - Surveys must be completed during the appropriate window for each time point. Site study staff can either mail the follow-up surveys to the subjects OR at the end of one visit, they can provide the next round of surveys to the subjects to take home with them for the next follow-up visit.
 - Ideally subjects will complete the survey packet at home and bring to site study staff on the day of a routinely scheduled visit for the oncology physician visit or designee (e.g., nurse practitioner) or cancer treatment.
 - If the patient needs assistance from site study staff to complete surveys on-site, allow adequate time (45-60 minutes).
 - If patients and caregivers cannot complete packet at home:
 - Patient and caregiver can come in prior to office visit to complete surveys.
 - Patient and caregiver can complete surveys during cancer treatment visits (e.g., chemotherapy infusion).
 - If needed, the patient and caregiver can meet with the site study staff at an additional time to complete the follow-up surveys. The subjects do not need to meet with the oncology physician to complete the surveys.

11.4.1b. AT EACH SCHEDULED FOLLOW-UP VISIT:

- *Staff* will administer the following assessments to the patient:
 - Cognitive and Physical Performance.
 - If depression (GDS) assessment score ≥ 11 , both usual care arm and intervention arm inform patient's oncology physician with template as per training.
- *CRA*: Complete all CRA follow-up study forms. CRAs at practice sites randomized to the **intervention arm** will complete the GA-Recommendation Follow-up forms by comparing them to the GA-Recommendation Baseline forms, clinic note, and referring to the oncology physician (if needed).
- *Patient*: Complete all surveys in the follow-up packet.
- *Caregiver*: Complete all surveys in the follow-up packet.
- Site study staff will submit the following to the URCC Research Base:
 - All oncology physician, patient and caregiver surveys from above.
 - All CRA study forms.

11.4.1c. A subset of the chart notes will be requested if there are discrepancies or missing information in key data.

11.5. Telephone Team Call (1 to 7 days from Baseline)

The Telephone Team will consist of University of Chicago and University of Rochester research staff and will be blinded to group assignment. The Telephone Team will make a phone call to the patient subject within 1 to

7 days, or up to 2 weeks, of the baseline clinic consultation to assess patient satisfaction with communication about age-related issues and concerns. The phone call will be recorded.

11.5.1. BEFORE THE PHONE CALL:

11.5.1a. Site Study staff will provide the patient subject’s preferred and alternate phone numbers, best time to call, and mailing address as part of the registration process for the patient. Caregiver phone number will be obtained as a back-up.

11.5.1b. To ensure that the Telephone Team remains blinded to the patient’s group assignment, the Telephone Team will obtain the contact information (phone number and mailing address) from the URCC Research Base.

11.5.1c. The study materials will be mailed (with a return envelope provided) to the patient by the Telephone Team if a telephone call is not feasible (e.g., due to sensory or disability impairments).

11.5.2. DURING THE PHONE CALL:

11.5.2a. The Telephone Team will administer the Health Care Climate Questionnaires to the patient. Telephone Team will submit the Health Care Climate Questionnaires to the URCC Research Base and keep a copy labeled with patient identification number on site.

12. REIMBURSEMENT

In order to improve study retention and compliance, we will compensate patients and caregivers for their participation (i.e., time and travel). Patient and caregiver subjects will each receive \$15.00 for every time point assessment completed. Both patients and caregivers can receive up to \$60.00 each if all four time point assessments are completed.

13.7. ONLY serious adverse events related to the study procedures need to be reported for data and safety monitoring purposes. AEs and SAEs related to routine oncology treatment and care DO NOT need to be reported.

13.8. Adverse events should be reported to the local IRB as per their requirements.

13.9. Data Safety and Monitoring

13.9.1. All adverse events requiring reporting will be submitted to the Research Base as described in section 13.4. Adverse events that are *serious AND unexpected AND related* will be forwarded to the study chair and the URCC Data Safety and Monitoring Committee (DSMC) chair immediately upon receipt at URCC. Additional information may be requested upon their review.

13.9.2. All adverse events reported to URCC are entered into a protocol-specific spreadsheet. Adverse event rates are monitored utilizing the spreadsheet. If a serious adverse event is being reported frequently, the study chair will conduct a detailed review. The DSMC Committee Chair will be notified and will determine if further action is required.

13.9.3. The URCC Data Safety Monitoring Committee (DSMC) will review study progress and cumulative reports of adverse events at annual meetings. An overall assessment of accrual and adverse events will enable the committee members to assess whether significant benefits or risks are occurring that would warrant study closure.

13.9.4. The URCC will notify the NCORPs immediately of any serious safety concerns identified by the DSMC. DSMC reports will be available for download on the research base website.

14. CRITERIA FOR WITHDRAWAL

Subjects who discontinue or are withdrawn from study will be asked to complete all assessment forms up until the time of withdrawal.

If an oncology physician withdraws from the study, no further patients with this oncology physician will be recruited. Whenever possible, patients who have already been enrolled should complete study procedures and their data will be included in the analyses.

Participation in this study is voluntary. Participants are free not to take part or to withdraw at any time, for whatever reason, without risking loss of present or future care they would otherwise expect to receive. In the event that a patient does withdraw from the study, the information they have already provided will be kept in a confidential manner. Participants may discontinue participation in the study at any time if they decide they do not wish to take part any longer. Participants may be withdrawn from the study by research personnel if it is deemed in their best interest to no longer participate.

15. STATISTICAL PLAN

15.1. Statistical Considerations

[figure not shown]
This is a cluster-randomized trial with NCORP practice sites being the clusters. Because of the cluster randomized study design, we will apply linear mixed model methodology.¹⁰⁴ The outcome will be the response, and the arm will be the fixed effect. NCORP practice sites will be entered as a random effect independent of residual error. Estimation will be performed using Restricted Maximum Likelihood, and the null hypothesis of zero mean difference between arms will be tested using a F test.¹⁰⁵ The specific NCORP practice site differences will be assessed graphically using Best Linear Unbiased Predictors (BLUP) of the mean response for each NCORP.

All regression analyses will include terms to control for study site and oncologist type. In addition, clinically important socioeconomic variables such as patient gender, age, race/ ethnicity, and cancer variables such as cancer type and treatment status will be used to control for patient-level covariates. In case a key covariate is found to be unbalanced between study arms, it will be included in the model as a potential confounder.

15.2. Sample Size for NCI-Specified Primary Aim

We will utilize the modified HCCQ to address patient satisfaction with communication regarding age-related issues. Based on an analysis of the VOICE study, the standard deviation estimate of HCCQ was 2.1. The Intraclass Correlation (ICC) was 0.14 with a 95% confidence interval from 0.01 to 0.51. Because of the large amount of uncertainty in the ICC, we calculated power curves for $ICC=\{0.01, 0.14, 0.51\}$, with $ICC=0.51$ being the most conservative. This design (8 sites per arm and 31 subjects per site) has 80% power at the 0.05 significance level to detect a change in HCCQ of 0.6, 1.3 and 2.3 for $ICC=\{0.01, 0.14, 0.51\}$, respectively. Since the best estimate of the ICC is 0.14, the expected detectable difference is 1.3. This corresponds to an effect size of 0.62. The range of the HCCQ scores (modified HCCQ for satisfaction with age-related discussions) is 7 (worst possible) to 35 (best possible). The figure to the right shows the power for a range of detectable differences (D) for $ICC=0.01, 0.14$ and 0.51 (Figure 3). As mentioned in Section 7.1, small changes in satisfaction scores have been interpreted in other studies to be meaningful given a focus on achievement of high satisfaction scores and the link with reimbursement. In addition to using the total score as a continuous variable, we will compare the results for each question as a dichotomous variable (5 vs <5). If the distribution is skewed, we will consider treating the scores as an ordinal variable in analyses.

Figure 3: Sample Size for NCI-specified Primary Aim

Accounting for a small dropout rate of 5% (based on our observational cohort data¹), the targeted accrual will be **528 patient subjects total**. The dropout rate reflects patients who sign consent but withdraw prior to the audio-recorded baseline visit and capture of the modified HCCQ (which will occur within 7 days of baseline visit).

[figure not shown]
During NCORP site recruitment, if more than 16 NCORP sites are interested in participating, we will allow randomization. As of February 1, 2017, we have 68 practice sites participating in the COACH study; the increased practice site clusters provide improved statistical power. The total patient sample size will stay the same, and accrual will cease when that target is met.

Analysis for Primary Aim 1. This is a cluster randomized trial with NCORP practice sites being the clusters. Because of the cluster randomized study design, we will apply linear mixed model methodology.¹⁰⁴ The total modified HCCQ scores (HCCQ-age) will be the response, and the arm will be the fixed effect. NCORP practice sites will be entered as a random effect independent of residual error. Estimation will be performed using Restricted Maximum Likelihood, and the null hypothesis of zero mean difference between arms will be tested using the F test.¹⁰⁵ The specific practice site differences will be assessed graphically using Best Linear Unbiased Predictors (BLUP) of the mean response for each site.

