1.8. Preliminary Data

The investigative team is poised to build upon a considerable body of prior work. The research team has conducted studies that have demonstrated the high prevalence of health status issues that could influence cancer outcomes in older patients.^{15,16} They have developed a GA tool for older persons with cancer and the feasibility of this tool has been studied in hundreds of cancer patients in multicenter clinical trials.^{1,7,54} They have collaborated on a prospective multicenter study to quantify the risks of chemotherapy among older adults with cancer.¹ [name] has pilot-tested GA and GA-driven interventions with 200 patients from her geriatric oncology clinic.⁷¹ Drs. [name], [name], and [name] have experience in the study of communication in oncology. Other investigators

lend significant interdisciplinary expertise and stakeholders (CARG, an advisory board of older patients with cancer, advocates and caregivers, and community oncology physicians) have provided significant input at all stages of preliminary work.

Of importance, [name] and [name] collaborate on a NCI-funded study (R01 NIH/1R01CA140419-01A1), which evaluates whether a communication coaching intervention that targets oncology physicians, patients and caregivers improves discussions regarding prognosis and treatment choices in advanced cancer. The primary outcome for this study (physician communication behaviors) was obtained from clinic consultations that are audio-recorded. The patients (n=81 older patients) also completed a measure of patient satisfaction (Health Care Climate Questionnaire), which provided preliminary data for sample size calculations for the current proposal as the primary outcome.

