7.1. NCI-specified Primary Outcome

The Health Care Climate Questionnaire (HCCQ) ⁸²⁻⁸⁵ measures patient-centered autonomy-supportive physician behaviors and satisfaction with communication such as whether the patient and caregiver feel that the physician understands his/her perspective, provides choices and options, and encourages participation in decisions. The measure has been studied and validated in older patients. Similar to other studies which adapt satisfaction scales to capture specific clinical criteria (e.g., satisfaction with the physician regarding communication about chemotherapy),⁸⁶ the HCCQ has been modified for this study (HCCQ-age) to specifically address patient satisfaction with oncology physician behaviors and communication regarding age-related issues and concerns in order to specifically address satisfaction with the intervention (geriatric assessment summary and recommendations) rather than satisfaction with other aspects of cancer care (e.g., communication about cancer treatment). As is done with satisfaction with care surveys in other research and in clinical settings, the HCCQ (both modified and original) will be administered within 1 to 7 days after the baseline audio-recorded clinic visit.⁸⁷⁻⁹⁰ These measures will be obtained via a phone call administered by trained personnel (or mailed if a telephone call within 2 weeks of the baseline visit is not feasible). If this is not completed, the 4-6 week visit HCCQ data will be used in its place. Our University of Chicago collaborators ([name] and [name]) have experience with the conduct of such assessments over the phone and this minimizes perceived or real influence from the oncology physician or Research Base. The University of Chicago collaborators and research staff, who are subcontracted through PCORI, will be blinded to group assignment as the Telephone Team. Press-Ganey measures of satisfaction of overall care will be collected at week 4 and in follow up visits. The HCCQ will also be completed as part of the patient and caregiver packets in follow up time points for comparison.

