[name] research team has extensive experience^{76,85} with the use of the HCCQ and has captured this measure in 81 patients similar to those who will be recruited for the proposed study (older patients with advanced cancer). Patients were recruited to a NCI-funded study that is evaluating a coaching intervention to improve physician communication behaviors.⁹¹ Because the study utilizes a cluster randomized design, an intracluster correlation coefficient (ICC) was estimated from existing data to assist with sample size calculations for the current proposal. HCCQ has 5 questions measured on a Likert scale of 1-5, which are added to create a score between 5-25. Ceiling effects are common with HCCQ and with patient satisfaction scales in general, although the modified version likely has less of a ceiling effect due to its focus on a specific clinical scenario. Despite the ceiling effects, policy makers have utilized patient satisfaction as a key measure for reimbursement in clinical practice, with a focus on obtaining "perfect" scores.

For example, the Hospital Value-Based Purchasing (VBP) Program⁹² is a Centers for Medicare & Medicaid Services (CMS) initiative established by the Affordable Care Act of 2010 to reward acute-care hospitals with incentive payments for the quality of care they provide to people with Medicare. Incentive payments are funded by a withhold of 1-2% of each hospital's base operating DRG payments for each patient discharge over a year, placing hospitals "at risk" for this amount based upon performance on quality measures. It is estimated that roughly half of participating hospitals will receive a net decrease in payments, while the remainder will receive a net increase in payments resulting from superior performance. The HCAHPS (Hospital Consumer Assessment of Healthcare Providers and Systems) survey, which is the first national, standardized, publicly reported survey of patients' perspectives of hospital care, represents the performance measurement for the VBP Patient Experience of

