9. NCORP PRACTICE SITE RANDOMIZATION

A practice site is defined as any practice location within an overarching NCORP designation where oncology physicians and study staff work independently, i.e., do not cross over into another site. Practice sites will be randomized to one of the two study arms by means of a computer-generated randomization table. The randomization process will be determined using R software provided by [name], the lead biostatistician of the URCC NCORP Research Base.

Sites are randomized on a continual basis due to a variety of factors (i.e., a new NCORP Community Affiliate has been added to the URCC NCORP Research Base network, a new oncology practice site has been added to an existing NCORP Community Affiliate, or an oncology practice site that is currently affiliated with an NCORP Community Affiliate has expressed interest in participating in the COACH study). Past accrual to URCC studies (or NCORP Cancer Control studies if URCC accrual information is not available for new Affiliates and sites) is used to stratify each practice site as a **large** accruing (20 or more accruals/year) site or a **small** accruing (less than 20 accruals/year) practice site in order to assure balance in the randomization. The general assumption will be that any new site will be considered "small", unless it is determined based on past accruals that they are large. For new oncology practice sites that meet the definition for being independent (i.e., physicians and staff that do not cross over into another site), the next unassigned randomization allocation, from the randomization table will be used to assign their study arm. The randomization table takes into account size of the practice site. If a new oncology practice site is added at a later time during the study with physicians/staff that also see patients (cross over) at both or multiple practice sites, the new practice site will be assigned to the same study arm as the already randomized practice site where the physician/staff also sees patients.

Once sites have IRB approval on file with the Research Base and at least one member of research staff is trained on all study procedures, they are notified of their randomization allocation by an email from the study PI, [name]. Practice sites names and randomization assignments are saved in the database, this is used to link to which arm each study patient belongs to during patient registration.

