The original sample size calculation (Section 15) was based on the randomization of the 16 NCORP oncology practice sites. During study startup, as the structure of the new NCORP affiliates unfolded, more practice sites than was anticipated were interested in participating. The original protocol included the ability for more sites to participate, since the increase in the number of the clusters also increases the statistical power of the study.

[figure not shown]

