#### 3.4.1 Sample Size for NIH-specified Primary Aim

We will utilize the modified HCCQ to address patient satisfaction with communication regarding age-related issues (HCCQ-age). Based on an analysis of the VOICE study, the standard deviation estimate of HCCQ was 2.1. The Intraclass Correlation (ICC) was 0.14 with a 95% confidence interval from 0.01 to 0.51. Because of the large amount of uncertainty in the ICC, we calculated power curves for ICC={0.01, 0.14, 0.51}, with ICC=0.51 being the most conservative. This design (8 sites per arm and 31 subjects per site) has 80% power at the 0.05 significance level to detect a change in HCCQ of 0.6, 1.3 and 2.3 for ICC={0.01, 0.14, 0.51}, respectively. Since the best estimate of the ICC is 0.14, the expected detectable difference is 1.3. This corresponds to an effect size of 0.62. The range of the HCCQ-age scores is 7 (worst possible) to 35 (best possible). Analyses will be based on the HCCQ variables being a continuous variable. We will use a generalized mixed model to confirm robustness. The sample size figure below shows the power for a range of detectable differences (D) for ICC=0.01, 0.14 and 0.51. Small changes in satisfaction scores have been interpreted in other studies to be meaningful given a focus on achievement of high satisfaction scores and the link with reimbursement. In addition to evaluating HCCQ-age using the total score as a continuous variable, we will compare the results for each question as a dichotomous variable (5 vs <5). If the distribution is skewed, we will consider treating HCCQ-age as an ordinal variable in analyses.

Accounting for a small dropout rate of 5% (based on our observational cohort data), the targeted accrual will be **528 patient subjects total**. The dropout rate reflects patients who sign consent but withdraw prior to the audio-recorded baseline visit and capture of HCCQ-age (which will occur within 7 days of baseline visit). To date out of 479 evaluable patients we currently have received 407 baseline HCCQ-ages; 4-6 week HCCQ-ages will be substituted per protocol for 33 patients; there are 19 patients that have no baseline HCCQ-age because they either died or withdrew before the 4-6 week visit, this brings us to a current total of 440 baseline HCCQs to be used in the per protocol analysis.

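### SAP 4.2 names HCCQ where the primary outcome is HCCQ-age, and the 1.3-point detectable difference is a 16-site figure for the earlier study's HCCQ that was not restated

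*Protocol*

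**What the plan says.** **Which score is primary.** Protocol 15.2 (analysis for Primary Aim 1) and SAP 2.3.1 name the modified questionnaire, HCCQ-age. SAP 4.2 names the total HCCQ score as the response, and SAP 4.4.3 also says HCCQ where the matching text under Protocol 15.4.3 says HCCQ-age. Both instruments are collected: Protocol 7.1 states that "the HCCQ (both modified and original) will be administered within 1 to 7 days after the baseline audio-recorded clinic visit". They have separate rows in the patient measures tables (Protocol Appendix X-1; SAP 3.7.1) and separate entries in the SAP abbreviations.

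**Detectable difference.** Protocol 15.2 and SAP 3.4.1 use the same inputs: "Based on an analysis of the VOICE study, the standard deviation estimate of HCCQ was 2.1", ICC 0.14 (95% CI 0.01 to 0.51), 8 sites per arm and 31 patients per site. They report 0.6, 1.3 and 2.3 points for ICC 0.01, 0.14 and 0.51, and an effect size of 0.62. Protocol 1.8 says that older patients in the earlier study "completed a measure of patient satisfaction (Health Care Climate Questionnaire), which provided preliminary data for sample size calculations". Protocol 7.1 describes that instrument: "HCCQ has 5 questions measured on a Likert scale of 1-5, which are added to create a score between 5-25". The range printed beside 1.3 points is 7 to 35, the range of HCCQ-age.

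**Number of sites.** Protocol 9: "The original sample size calculation (Section 15) was based on the randomization of the 16 NCORP oncology practice sites". Both documents then report 68 practice sites at 1 February 2017 and an unchanged total of 528 patients, and say only that power improves.

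**The concern.** There are two separate problems.

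First, a programmer who follows SAP 4.2 literally would analyse a different collected score from the one the protocol makes primary.

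Second, 1.3 points does not describe the trial being run. It belongs to an instrument described as scored 5 to 25, while the primary outcome is scored 7 to 35. Protocol 7.1 itself expects the distribution to differ: "the modified version likely has less of a ceiling effect due to its focus on a specific clinical scenario". It also belongs to 16 sites rather than 68. The two omissions pull in opposite directions. A longer scale probably has a larger SD, which raises the detectable difference in points; more clusters lower it. A reader therefore cannot tell from the text what HCCQ-age difference the trial can detect. Protocol 15.2 argues that small score changes are meaningful, so the figure should be on the scale that will be reported.

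**Working it through.** **1. The score named, place by place**

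- Protocol 15.2, analysis for Primary Aim 1: HCCQ-age
- SAP 2.3.1, primary aim: HCCQ-age
- SAP 4.2, primary analysis: HCCQ
- Protocol 15.4.3, correlation with number of discussions: HCCQ-age
- SAP 4.4.3, same analysis: HCCQ

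SAP 3.4.1 counts 407 baseline HCCQ-age forms plus 33 substituted from 4-6 weeks, and then calls the 440 HCCQs. So the SAP does use the short name loosely.

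**2. Reproducing the plan's figures**

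Detectable difference = δ × SD × √(4 × DE / N), with DE = 1 + (m − 1) × ICC. N is the number of evaluable patients and m the number per unit. δ is the noncentrality giving 80% power for a two-sided 0.05 t test with (units − 2) df. The documents do not state sidedness; two-sided reproduces their figures.

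16 units, m = 31, N = 496, SD 2.1, 14 df, δ = 3.013:

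- ICC 0.01: DE = 1.30, giving 0.648 (stated 0.6)
- ICC 0.14: DE = 1 + 30 × 0.14 = 5.2; standard error 2.1 × √(4 × 5.2/496) = 0.430; 3.013 × 0.430 = 1.296 (stated 1.3)
- ICC 0.51: DE = 16.3, giving 2.294 (stated 2.3)

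Effect size 1.3/2.1 = 0.62. Accrual: 31/0.95 = 32.6, rounded up to 33; 33 × 16 = 528. All agree with the plan.

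**3. 68 units** (assumed independent and equal in size, N = 496)

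m = 496/68 = 7.29; at ICC 0.14, DE = 1 + 6.29 × 0.14 = 1.88; 66 df, δ = 2.843. Standardised difference 2.843 × √(4 × 1.88/496) = 0.35 SD. At SD 2.1 this is 0.74 points (0.55 at ICC 0.01; 1.10 at ICC 0.51).

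**4. An illustrative SD for HCCQ-age**

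The documents give none. Assumption: seven items that behave like the original five, with common inter-item correlation r. The SD ratio is √[7(1 + 6r) / (5(1 + 4r))].

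- r = 0: 2.1 × 1.183 = 2.48
- r = 1: 2.1 × 1.4 = 2.94

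This range is not a bound, because it ignores the weaker ceiling effect that the protocol expects.

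| Units (equal size) | ICC | SD 2.48 | SD 2.94 |
|---|---|---|---|
| 16 | 0.14 | 1.53 | 1.81 |
| 68 | 0.01 | 0.65 | 0.77 |
| 68 | 0.14 | 0.87 | 1.03 |
| 68 | 0.51 | 1.30 | 1.54 |

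The plan's own figure at ICC 0.51 is 2.3.

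**5. Unequal site sizes**

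In the planned mixed model, a site of size n contributes information proportional to n / (1 + (n − 1) × ICC), so large sites are down-weighted. With 68 units and an assumed size CV of about 1, the detectable difference at ICC 0.14 is about 0.38 SD. That is 0.38 × 2.48 = 0.94 to 0.38 × 2.94 = 1.12 points.

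**6. When 1.3 points would be missed** (ICC 0.14, equal sizes, N = 496)

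- 80% power at 1.3 points needs at least 24 units at SD 2.48, or 34 at SD 2.94.
- With 68 units, the SD would have to exceed 1.3/0.350 = 3.7.

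**The case against.** No printed figure for the primary aim is wrong, and the sources are named: both documents cite the earlier study and the 8 × 31 design, and Protocol 9 and SAP 3.3.4 call the calculation the original one for 16 sites. Borrowing the inputs was reasonable at design. The patient total, the test and the conduct do not depend on the missing figure, and 1.3 is conservative if there are 68 independent units with an SD in the illustrated range. All of this stands, and it is why the power restatement is minor.

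A reader might infer that the trial is underpowered. The documents do not support that: at ICC 0.14 it would take far fewer than 68 independent units, or an SD above about 3.7, to miss 1.3 points with equal sites.

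A reader might also infer that there are far fewer than 68 independent units. There are grounds for caution. When a site added later shares physicians or staff with one already randomised, "the new practice site will be assigned to the same study arm as the already randomized practice site". The SAP allocation table repeats some randomisation IDs over many rows, and a footnote to SAP Appendix D provides for clusters that enrolled nobody. But that table is labelled a sample, and the count may appear in figures that are missing from the text available here. The number is unknown, not shown to be small.

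Finally, a reader might take SAP 4.2 as a change of primary outcome. SAP 2.3.1 and the loose usage in SAP 3.4.1 make a slip far more likely. That explains the wording; it does not make it safe to leave.

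**Conclusion.** The point holds in two parts of different weight.

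The wording of SAP 4.2, and likewise of SAP 4.4.3, should be fixed. Read literally, SAP 4.2 selects a score that is collected but is not the primary outcome.

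The power statement is correct for its own inputs but does not describe the trial. Both 1.3 points and 0.62 SD are 16-site figures; only the second is free of the scale, and it still needs ICC 0.14 to carry over to HCCQ-age. For 68 independent units and 496 patients at ICC 0.14, the figure is 0.35 SD with equal sites and about 0.38 SD with a size CV near 1. In points that is 0.87 to 1.03 and 0.94 to 1.12 respectively, under the illustrative SD. The HCCQ-age SD and ICC, and the number and sizes of independent enrolling units, are not in the surviving text, so the real figure could be better or worse than 1.3. This is a minor gap in reporting and is not evidence of inadequate power.

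**What to change.** 1. In SAP 4.2 and 4.4.3, replace HCCQ with HCCQ-age.
2. Estimate the SD and ICC of HCCQ-age arm-blind from the 407 baseline forms that SAP 3.4.1 reports. A blinded estimate absorbs any arm effect, so it errs on the conservative side. For example, a true 1.3-point effect adds 1.3²/4 = 0.42 to the between-site variance. At SD 2.48 (variance 6.17; between-site part 0.14 × 6.17 = 0.86), the ICC would appear as (0.86 + 0.42)/(6.17 + 0.42) = 0.19.
3. In Protocol 15.2 and SAP 3.4.1, state the number and sizes of the independently randomised units that enrolled patients. Restate the detectable difference on the 7 to 35 scale for those units, using the mixed-model variance.
4. Label both 1.3 points and 0.62 SD as the original 16-site figures from the earlier study's HCCQ.

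The cost is a few sentences in each document and one blinded estimate from data in hand. It needs no extra patients and no change to conduct or to the primary test.
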